Any additional abbreviations used within the protocol must also be added here.

ACCORD	Academic and Clinical Central Office for Research & Development - Joint office for The University of Edinburgh and Lothian Health Board
AE	Adverse Event
AR	Adverse Reaction
СІ	Chief Investigator
СК	Creatinine Kinase
CRF	Case Report Form
CSU	Catheter Specimen Urine
CSR	Clinical Study Report
СТА	Clinical Trial Authorisation
СТІМР	Clinical Trial of Investigational Medicinal Product
СТБ	Cardiotocography
DMC	Data Monitoring Committee
DSUR	Development Safety Update Report
ECTU	Edinburgh Clinical Trials Unit
EDD	Estimated Date of Delivery
EudraCT	European Clinical Trials Database
GCP	Good Clinical Practice
GMP	Good Manufacturing Practice
HELLP	Haemolysis, elevated liver enzymes and low platelets
IB	Investigator Brochure
ICH	International Conference on Harmonisation
IMP	Investigational Medicinal Product
ISF	Investigator Site File
ISG	Investigational Supplies Group
ISRCTN	International Standard Randomised Controlled Trials Number
LFTs	Liver Function Tests

CR007-T01 v4.0 PIPIN Protocol Version 5.0 17/05/2019 Page **7** of **45**

LLETZ	Large Loop Excision of the Transformation Zone	
LPS	Lipopolysaccharide	
LVS	Low Vaginal Swab	
MHRA	Medicines and Healthcare products Regulatory Agency	
MSU	Mid-Stream Urine	
NICE	National Institute for Health and Care Excellence	
PI	Principal Investigator	
PIL (PIS)	Patient Information Leaflet (Sheet)	
NIMP	Non-Investigational Medicinal Product	
QA	Quality Assurance	
QMRI	Queen's Medical Research Institute (Edinburgh)	
QP	Qualified Person	
RCOG	Royal College of Obstetricians and Gynaecologists	
REC	Research Ethics Committee	
ROM	Rupture of Membranes	
SAE	Serious Adverse Event	
SAR	Serious Adverse Reaction	
SDV	Source Data Verification	
SPC	Summary of Product Characteristics	
SOP	Standard Operating Procedure	
SUSAR	Suspected Unexpected Serious Adverse Reaction	
TMF	Trial Master File	
TMG	Trial Management Group	
TSC	Trial Steering Committee	

CR007-T01 v4.0 PIPIN Protocol Version 5.0 17/05/2019 Page **8** of **45**

TRIAL SUMMARY

Trial Title	A Feasibility Study Investigating P ravastatin for the Prevention of P reterm Birth in Wome n
Study Acronym	PIPIN
Clinical Phase	Phase II
Trial Design	Randomised Control Trial
Trial Participants	Pregnant patients presenting in preterm labour between 24+0- 35+6 weeks gestation
Planned Number of Participants	40
Planned Number of Sites	Initially single site, but may be extended to multi-site should this be required for recruitment
Countries Anticipated to be Involved in Trial	Scotland
Treatment Duration	7 days
Follow up Duration	28 days post estimated date of delivery
Total Planned Trial Duration	2 years
Primary Objective	To evaluate the feasibility of recruitment of patients in preterm labour to a randomised controlled trial
Secondary Objectives	Evaluate pravastatin for use in preterm labour to prolong pregnancy, reduce contraction frequency and lower maternal and fetal markers of inflammation. Identify any adverse effects associated with use of Pravastatin in preterm labour. Observation of average time from presentation of the participant to first dose of treatment received, acceptability of the trial and compliance with 7 days of blinded treatment. To perform pharmacokinetic studies of pravastatin in pregnancy
Primary Endpoint	Recruitment, retention and outcome collection of 40 Participants in established preterm labour

	1) Retention, adherence and ability to collect clinical
	outcomes from participants
	2) Time to delivery from presentation and gestation at
	delivery
	3) Contraction frequency from presentation to delivery or
	cessation of regular uterine activity.
	 Maternal markers of inflammation including, but not limited to: IL-6, IL-10, IL-13, IL-17, TNFa, IL-1RA, sTNF-
	RI, sTNF-R2, and HO-1, as well as levels of the soluble
	IL-6R and the inhibitor spg130 (abbreviated hereafter to
	'Inflammatory Profile')
	5) Fetal measures of inflammation (cord IL-1, IL-6, IL-8) as
	well as levels of sIL-6R and sgp130.
	6) Adverse events (maternal and fetal)
	7) Time from 'time first seen' to delivery of first dose of trial
	medication
	8) Compliance with 7 days of blinded treatment
	9) Acceptability of the trial to those who have participated
Secondary Endpoints	10) Pharmacokinetic parameters as compared with current
	published data
	11) Maternal outcomes: a. Proven maternal infection
	b. Safety of intervention to mother (self-reported)
	AEs and biochemical monitoring of liver function
	tests and creatinine kinase).
	c. Pre-labour ROM
	d. Duration, location and level of care of hospital
	stay following presentation with suspected
	preterm labour AND following delivery.
	12) Neonatal outcomes:
	a. Details of in utero transfers including mode of
	transport required
	b. Gestational age at delivery, morbidity and
	mortality, birthweight, duration and location of
	hospital stay post-delivery and up to 28 days post EDD.
	c. Safety of intervention
IMP(s)	Pravastatin 40mg Tablets, Teva UK LTD (encapsulated)
	Placebo 40mg capsules
IMP Route of Administration	Orally
NIMP(s)	Nil

Lay Summary of Trial	Preterm birth contributes to around 11% of all births worldwide and is the major cause of infant morbidity and mortality. Whilst in the UK survival of babies born preterm has improved, the proportion of survivors without long term developmental problems has not, and current treatments are ineffective at preventing this. This study aims to see whether women in preterm labour would be willing to be randomised to take a tablet (pravastatin) or placebo. Preterm labour is known to be due to both inflammation within the womb and contractions. Pravastatin in an anti-inflammatory agent which has been used safely in pregnancy, and which appears in in animal studies to reduce preterm labour associated events.
	We hope if women are willing to accept this trial and participate, this will help us develop a larger clinical study to find a new treatment for preterm labour.

1. INTRODUCTION

1.1 BACKGROUND

Spontaneous preterm labour is the biggest cause of preterm birth (Norman et al. 2009). Preterm birth is itself the major cause of infant mortality and morbidity, accounting for 11% of births worldwide (Blencowe et al. 2012). It is estimated that nearly one million children every year have neurodevelopmental disability as a direct consequence of preterm birth (Blencowe et al. 2013), with pulmonary, cardiac and gastrointestinal dysfunction all described in surviving infants (Rubens et al. 2014)

The aetiology of preterm birth remains an incompletely understood process, with roughly 75% occurring spontaneously in the UK (the remainder being iatrogenic for maternal or fetal reasons) (Rubens et al. 2014). Known aetiological factors contributing to preterm birth include infection and inflammation, uteroplacental haemorrhage or ischaemia, or uterine over distension such as in the multiple pregnancy(Goldenberg et al. 2008). There are also several well described clinical risk factors including previous preterm birth

Currently available treatments options include antibiotics, tocolysis and magnesium sulphate (for fetal neuroprotection as opposed to arrest of labour).(Preterm labour and birth | Guidance and guidelines | NICE n.d.) Unfortunately neither antibiotics nor tocolysis have been shown to provide short term benefit to both the mother and fetus (only in certain circumstances), and no long term benefit to children born at 37 weeks gestation or less (Flenady et al. 2013, Haas et al. 2012).

Magnesium sulphate, whilst recommended by NICE for fetal neuroprotection, does not prevent preterm labour. (Preterm labour and birth | Guidance and guidelines | NICE n.d.)

As considerable evidence implicates inflammatory mediators in both the underlying mechanisms of parturition (term and preterm), and initiation of brain damage which leads to neurodevelopmental disability associated with preterm delivery (Boyle et al. 2017), it follows that the ideal agent for the treatment of preterm labour would be one which both inhibits myometrial contractility and conveys anti-inflammatory benefit. Our *in vitro* and pre-clinical *in vivo* studies suggest that statins have both actions. We hypothesise that statins may reduce preterm labour associated preterm birth AND reduce long term neurodevelopmental disability.

CR007-T01 v4.0 PIPIN Protocol Version 5.0 17/05/2019 Page **11** of **45**

Of the statins in current clinical use, we have selected pravastatin for this feasibility study as it now has an established safety profile in pregnancy. (Bateman et al. 2015) (Lefkou et al. 2016)(Costantine, Cleary, Hebert, Ahmed, Brown, Ren, Easterling, Haas, Haneline, Caritis, Venkataramanan, West, D'Alton, Hankins, and Eunice Kennedy Shriver National Institute of Child Health and Human Development Obstetric-Fetal Pharmacology Research Units Network 2016). Furthermore, when pravastatin was being investigated for potential use in both refractory anti-phospholipid syndrome and pre-eclampsia, pregnancy was prolonged in the treatment group (STAMP - ISRCTN23410175) (Lefkou et al. 2016).

1.2 RATIONALE FOR STUDY

In this trial, we are aiming to demonstrate the feasibility of a randomised controlled trial of statins versus placebo for women presenting in preterm (24+0 to 35+6 weeks gestation) labour.

As aforementioned, the treatment of preterm labour remains an unmet clinical need and current therapeutic options provide little short term benefit to both the mother and fetus (and only in certain circumstances), and no long term benefit to children born at 37 weeks gestation or less.

Statins in pregnancy

Statins are widely used to treat hypercholesterolaemia and coronary heart disease. Statins act by inhibiting cholesterol synthesis but have pleotrophic anti-inflammatory properties (Sirtori 2014). Until relatively recently, statins were contraindicated in pregnancy due to concerns about teratogenic effects. This is based on a 1983 study, when fetal skeletal malformations were observed in rats given toxic doses (800 mg/kg/day) of lovastatin, a highly lipophilic statin. (Minsker et al. 1983). However, this effect was not seen when hydrophilic pravastatin was administered to pregnant rats in doses up to 1000mg/kg/day (around x120 the dose used in patients based on surface area) (StAmP, ISRCTN23410175) Importantly, in human studies, there is little evidence to support this concern: a recent comprehensive prospective study of over 1000 women found no increase in congenital malformations in women who had taken statins when increased background risk due to maternal illness was corrected for (Bateman et al. 2015).

Whilst there have been some data suggesting an increased risk of the condition VACTERL (three or more of the following findings: vertebral, anal, cardiac, tracheal, oesophageal, renal, and limb defects), all of these cases (2 out of 52), the offending statin was lovastatin (lipophilic), and indeed all reports of congenital malformation following maternal statin exposure pertained to lipophilic statins (Edison and Muenke 2004). Furthermore, as the critical time period for organogenesis is first trimester, this is less relevant to our CTIMP where the intervention will specifically only be used above 24+0 weeks gestation.

Other trials using statins

Several trials have recently used Pravastatin in this pregnant population.

In the context of refractory antiphosphlipid syndrome, Pravastatin showed a pregnancy prolonging effect of pravastatin with no congenital abnormalities or late fetal deaths, and no evidence of maternal morbidity because of the use of pravastatin.(Lefkou et al. 2016). This is in keeping with a UK based biomarker efficacy study investigating the use of pravastatin for the severe form of pre-eclampsia. This will shortly report (6)(STAMP - ISRCTN23410175, manuscript in preparation). Whilst the STAMP trial showed that pravastatin did not affect levels of the primary outcome biomarker, it again prolonged pregnancy with no major safety issues ([name], personal communication).

Statins as therapies for preterm labour

CR007-T01 v4.0 PIPIN Protocol Version 5.0 17/05/2019 Page **12** of **45**

Anti-inflammatory effects

Pre-clinical studies have suggested that the statins pravastatin and simvastatin, administered to pregnant mice, exert anti-inflammatory effects within the feto-placental unit (Basraon et al. 2012). These feto-placental anti-inflammatory effects have been confirmed in human tissues by ourselves and others. For example, Basraon et al have shown that statins attenuate the production of pro-inflammatory cytokines induced by lipopolysaccharide (LPS) in a human fetal membrane explant model (Basraon et al. 2015). Additionally, in a myometrial cell line obtained from a pregnant woman, we show that 50µM simvastatin inhibits pro-inflammatory cytokine expression induced by LPS, AND that it inhibits LPS induced contractions.

Treatment of preterm labour in a pre-clinical model

Having shown that simvastatin exerts anti-inflammatory effects *in vitro*, we showed that simvastatin also reduces LPS induced IL-6 synthesis *in vivo* in a mouse model of preterm labour. Importantly, we also showed that simvastatin attenuates LPS induced preterm birth and pup death. These data demonstrate the significant potential of statins as effective treatments for preterm birth.

Pharmacokinetics and potency of statin formulations

There are a variety of formulations of statins each of which have different potencies, chemical structures, bioavailability, lipo/hydrophilicity, dependence on cytochrome P450 metabolism, cellular transport and pharmacokinetics (Sirtori 2014)(Bateman et al. 2015)(Egom and Hafeez 2016; Oliveira et al. 2016). Pravastatin was the statin chosen for the STAMP trial because its hydrophilicity means that placental transport (and hence fetal exposure to the drug) is likely to be minimal (Bedi et al. 2016). This assumption has largely been borne out in pharmacokinetic studies(Costantine, Cleary, Hebert, Ahmed, Brown, Ren, Easterling, Haas, Haneline, Caritis, Venkataramanan, West, D'Alton, Hankins, Eunice Kennedy Shriver National Institute of Child Health and Human Development Obstetric-Fetal Pharmacology Research Units Network, et al. 2016).

Furthermore, the pharmacokinetics of pravastatin compared with alternative statins (notably metabolism via chemical degradation in the stomach as opposed to via the cytochrome P450 enzyme chain, and dual elimination via both renal and hepatic routes) mean that there is a lower chance of drug interaction with required medications for the study group.

Benefits to participants

As this is a feasibility study, there is no direct proven benefit to participants. All Participants will receive the gold standard care for preterm labour as per local NHS guidelines. Importantly, where women will be recruited, we do not use any tocolysis, and erythromycin is only given to women with fetal membrane rupture (who would not be eligible for this study) so we do not anticipate any contradictions to usual practice due to involvement in this trial. Based on both our pre-clinical data, and data from the StAMP trail (STAMP - ISRCTN23410175), there may be some benefit from prolongation of pregnancy effect in the treatment arm of this trial.

2. STUDY OBJECTIVES

2.1 OBJECTIVES

2.1.1 Primary Objective

This CTIMP is a feasibility study of the acceptability of a randomised controlled trial of a statin or placebo for women in preterm labour.

CR007-T01 v4.0 PIPIN Protocol Version 5.0 17/05/2019 Page **13** of **45**

2.1.2 Secondary Objectives

Overall, the goal of this study is to inform design of a multicentre randomised controlled trial, and the secondary objectives are based on aspects of this.

- 1) To evaluate whether administration of pravastatin when compared with placebo to women in preterm labour is associated with prolonged time to delivery, a reduction in contractions, and lower maternal and fetal markers of inflammation without adverse effects.
- 2) To evaluate whether administration of pravastatin when compared with placebo to women in preterm labour improves maternal and fetal outcomes
- 3) To monitor the average time from a participant's first contact with medical staff to delivery of the first dose study drug.
- 4) To ascertain the acceptability of the study design to participants after completion of the protocol.
- 5) Record participant compliance with treatment
- 6) To describe the pharmacokinetics of pravastatin in the study population as compared with published parameters.

2.2 ENDPOINTS

2.2.1 Primary Endpoint

For this trial, the primary endpoint the proportion of patients presenting in preterm labour between 24+0 and 35+6 weeks gestation who consent to enter the trial.

2.2.2 Secondary Endpoints

Secondary Endpoints:

- 1) Retention, adherence and ability to collect clinical outcomes from participants
- 2) Time to delivery from presentation and gestation at delivery
- 3) Contraction frequency as monitored at presentation and from randomisation to delivery or cessation of regular uterine activity.
- 4) Maternal markers of inflammation including, but not limited to: IL-6, IL-10, IL-13, IL-17, TNFa, IL-1RA, sTNF-RI, sTNF-R2, and HO-1, as well as levels of the soluble IL-6R and the inhibitor spg130 (abbreviated hereafter to 'Inflammatory Profile')
- 5) Fetal measures of inflammation including but not limited to: (cord IL-1, IL-6, IL-8, sIL-6R and sgp130.
- 6) Adverse events (maternal and fetal)
- 7) Time from time first seen in an acute obstetric care setting to administration of trial medication as documented in the participant medical records.
- 8) Compliance with 7 days of blinded treatment
- 9) Acceptability of the trial to those who have participated
- 10) Pharmacokinetic parameters as compared with current published data
- 11) Maternal outcomes:
 - a. Proven maternal infection
 - b. Safety of intervention to mother (self-reported AEs and biochemical monitoring of liver function tests and creatinine kinase).
 - c. Pre-labour ROM
 - d. Duration, location and level of care of hospital stay following presentation with suspected preterm labour AND following delivery.
- 12) Neonatal outcomes:
 - a. Details of in utero transfers including mode of transport required
 - b. Gestational age at delivery, morbidity and mortality, birthweight, duration and location of hospital stay post-delivery and up to 28 days post EDD.
 - c. Safety of intervention

CR007-T01 v4.0 PIPIN Protocol Version 5.0 17/05/2019 Page **14** of **45**

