4. STUDY POPULATION

4.1 NUMBER OF PARTICIPANTS

We will to recruit 40 participants. Eligible participants are pregnant women presenting in preterm labour at 24+0 to 35+6 weeks gestation. Preterm labour is defined as regular uterine activity with either a positive fetal fibronectin (See Appendix 5) or evidence of cervical change as monitored through cervical length scanning or direct observation of dilation.

We estimate a duration of 2 years with an 18 month recruitment period. Follow up of participants to last Participant last visit will take up to another 6 months.

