5.5 RANDOMISATION

5.5.1 Randomisation Procedures

Participants will be randomised to active or placebo in a 1:1 ratio. Randomisation block size will use permuted blocks of size 2, 4, and 6, randomly sorted, and spliced with occasional randomly inserted simple runs of random length to aid unpredictability. Randomisation codes will be provided to ISG by ECTU, and packs dispensed in a sequential fashion from these. Details of the study pack number allocated will be recorded in the Participant's notes, on the medication record as well as in the drug accountability log in the treatment room of labour ward.

This trial will be double blinded. Randomisation codes will be held by both ECTU and the local Pharmacy department.

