10.2 PROPOSED ANALYSES

Measures to be reported:

Primary outcome data

1. Trial uptake: eligible participants as compared with recruitment.

Secondary Outcome Data

- 1. Routine participant demographics including past medical history and drug history
- Any additional treatments received during inpatient stay (including magnesium sulphate, antibiotics, syntocinon / other methods of induction/augmentation and steroids)
- 3. Retention, adherence and ability to collect clinical outcomes from participants
- 4. Time from presentation with threatened preterm labour to delivery of first dose of IMP.
- 5. Time from presentation to acute care and assessment services with suspected preterm delivery to delivery itself, as well as gestation at delivery
- 6. Contraction frequency during treatment course, from presentation to delivery or cessation of regular uterine activity.
- 7. Bloods: Liver function tests, creatinine kinase levels (side effects), maternal and cord inflammatory profile (see 2.2.2 for details of measures within the inflammatory profile).
- 8. Compliance with treatment
- 9. Adverse events
- 10. Acceptability of the trial following completion of the protocol
- 11. Other clinical outcomes
 - a. Maternal outcomes:
 - i. Proven maternal infection (See Appendix 4: Glossary of Terms for definition)

CR007-T01 v4.0 PIPIN Protocol Version 5.0 17/05/2019 Page **29** of **45**

- ii. Safety of intervention to mother (self-reported AEs and biochemical monitoring of liver function tests and creatinine kinase).
- iii. Pre-labour ROM
- iv. Duration, location and level of care of hospital stay following presentation with suspected preterm labour AND following delivery.
- b. Neonatal morbidity and mortality, safety of intervention, gestational age at delivery, birthweight, duration, location and level of care required following delivery. If in utero transfer occur, cause of method of transport used.
- 12. Pharmacokinetics of pravastatin

Participant uptake the study will involve a direct analysis of eligible participants presenting to acute care and assessment services compared with recruitment. Secondary outcomes 1 and 2 will be used to perform subgroup analysis and identify potential confounders between treatment and placebo arms. Outcomes 3 - 11 will be used to directly compare treatment and placebo arms of the trial, and inform design for a large scale trial in the future.

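### Time to delivery is compared between arms from presentation rather than randomisation, so it carries a variable pre-randomisation interval that treatment cannot affect (minor; wording fix)

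*Protocol*

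**What the plan says.** Section 2.2.2, item 2, gives the endpoint as "Time to delivery from presentation and gestation at delivery". The Trial Summary lists it with the same start. Section 10.2, item 5, repeats it as "Time from presentation to acute care and assessment services with suspected preterm delivery to delivery itself, as well as gestation at delivery".

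Section 10.2 then states that "Outcomes 3 - 11 will be used to directly compare treatment and placebo arms of the trial". That range includes item 5. It also includes item 4, the time from presentation to the first dose of study drug.

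The objective served is a randomised contrast. Section 2.1.2 asks whether pravastatin, compared with placebo, "is associated with prolonged time to delivery, a reduction in contractions, and lower maternal and fetal markers of inflammation without adverse effects".

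On the order of events:
- Sections 5.1 to 5.3 place eligibility testing, sometimes a cervical length scan or a wait for the trial team, and consent before randomisation.
- Section 5.2 calls the intervention time-critical but sets no limit on how long a woman may take to decide.
- Section 6.3 has the drug dispensed immediately after randomisation.
- Section 5.4 gives delivery before the first dose as an example of why a consented woman might not be randomised.

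**The concern.** A comparison of randomised arms should start when the arms come into being. Before randomisation there is no arm, no treatment and, for any woman who goes on to be randomised, no delivery. Starting at presentation adds to each woman's time a quantity that varies between women and carries no information about pravastatin.

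The starting event is also worded in several ways: presentation, time first seen in an acute obstetric setting, first contact with medical staff, and presentation with threatened or with suspected preterm labour. Randomisation is a single identifiable moment. Section 2.2.2, item 3, already uses it for contraction frequency, which is read at presentation and then followed from randomisation (although the Summary and section 10.2 word that endpoint from presentation).

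Item 4 of section 10.2 raises a related point. Time from presentation to first dose is complete before treatment can act, so in a double-blind trial any difference between arms is essentially chance. It is a feasibility measure for the whole cohort.

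What is at stake is modest but real. Section 10.1 names time to delivery among the data that will inform whether a large trial is warranted and feasible, and that trial could inherit the definition.

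**Working it through.** The protocol states no effect size, power or event count for time to delivery, so there is no figure to reproduce. The check asks how much the choice of origin could matter.

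**From the protocol.** Section 4.1: "We will to recruit 40 participants". Section 5.5.1: "Participants will be randomised to active or placebo in a 1:1 ratio". This gives about 20 per arm.

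**Assumed, not in the protocol.** Time from randomisation to delivery, T, is exponential with a true hazard ratio of 0.6 and a control median M of 2, 7 or 21 days. The delay from presentation to randomisation, D, is gamma (shape 2) with mean d of 3 to 48 hours, independent of arm. All women deliver. Two-sided alpha is 0.05.

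**Step 1: difference in means.** From presentation the time is Y = T + D. D has the same expectation in both arms, so

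E(Y₁) − E(Y₀) = (E(T₁) + d) − (E(T₀) + d) = E(T₁) − E(T₀).

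The origin cancels. In simulation with M = 7 days and d = 24 h, the difference was 6.52 days from either origin.

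**Step 2: ratio of means.** From randomisation it is 1/0.6 = 1.667. From presentation it is (E(T₁) + d)/(E(T₀) + d), where E(T₀) = M/ln 2 and E(T₁) = E(T₀)/0.6. For M = 2, E(T₀) = 2.885 and E(T₁) = 4.809 days, so:
- d = 0.25 day: 5.059/3.135 = 1.61
- d = 1 day: 5.809/3.885 = 1.50
- d = 2 days: 6.809/4.885 = 1.39

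| Control median | From randomisation | 6 h delay | 24 h delay | 48 h delay |
|---|---|---|---|---|
| 2 days | 1.667 | 1.61 | 1.50 | 1.39 |
| 7 days | 1.667 | 1.65 | 1.61 | 1.56 |
| 21 days | 1.667 | 1.66 | 1.65 | 1.63 |

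**Step 3: added variance.** Var(Y) = Var(T) + Var(D), with Var(D) = d²/2 under the gamma assumption. For control women with M = 2, Var(T) = 2.885² = 8.32. A 24 h delay adds 0.5 (6%) and a 48 h delay adds 2.0 (24%). With M = 7, Var(T) = 10.10² = 102, and a 24 h delay adds about 0.5%.

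**Step 4: hazard ratio.** Cox fits to 6,000 simulated women per scenario, using the same women for both origins, changed by 0.003 or less, with one exception: M = 2 days with a 48 h delay, where the estimate moved from 0.590 to 0.611. The reason is that, once most delays have elapsed, the hazard on the presentation scale returns to the hazard after randomisation. Only the earliest part of the curve is affected.

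**Step 5: power at 20 per arm.** The formula check is Φ(|ln 0.6| × √40/2 − 1.96) = Φ(1.615 − 1.96) = 0.365. Simulated log-rank power (4,000 runs) was about 0.34 to 0.35 from either origin. The worst case was a fall from 0.34 to 0.31, at M = 2 days with a 48 h delay.

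**The case against.** The strongest reply is that the consequence is slight. The delay comes before allocation and is independent of arm, so it favours neither. The absolute prolongation in days, arguably the natural scale for this question, is untouched. For delays of up to about a day the hazard ratio and the log-rank test are practically unchanged. The endpoint is secondary in an unpowered feasibility trial. At 40 events the 95% interval for a hazard ratio spans a factor of exp(1.96 × 2/√40) = 1.86 either way, which swamps a change in the third decimal place. Gestation at delivery, in the same endpoint item, does not depend on this clock at all. The pathway is also acute, with stock held on the labour ward, so long delays are unlikely. As for item 4, tabulating it by arm does no harm.

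All of that stands, and it limits the point to a minor one. It does not make presentation the right origin for a treatment comparison.

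A reader might infer more than the documents support, in three ways:
- **That the treatment effect is diluted in general.** It is not: dilution appears on ratio-of-time scales and as added noise, not in the difference in mean days.
- **That a Kaplan-Meier or Cox analysis from presentation would be invalid without delayed entry.** Under no treatment effect, Y has the same distribution in both arms, so the comparison remains valid. The protocol in any case names neither method and defers detail to the SAP.
- **That delays of several days should be expected, for example from repeat attendances.** The protocol gives no delay figure and describes nothing of the kind.

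**Conclusion.** The point holds as a minor fault of definition. The protocol fixes presentation as the origin in three places and compares arms on it, so an SAP that follows the protocol would inherit it. The event-free interval before randomisation follows from the order of events and needs no assumption.

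The size does rest on assumptions. It matters for ratios of means or medians when delivery follows quickly: a true ratio of means of 1.667 becomes 1.50 with a 24-hour delay and a 2-day control median. It is close to negligible when time to delivery is measured in weeks. The figures depend on exponential times, a true hazard ratio of 0.6 and illustrative delays, none of which come from the protocol. The actual delay is unknown, and the effect is probably small.

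**What to change.** - In the Trial Summary, section 2.2.2 (item 2) and section 10.2 (item 5), define the between-arm endpoint as time from randomisation to delivery. Gestation at delivery can stay as it is.
- Keep presentation-to-delivery and presentation-to-first-dose as descriptive feasibility measures for the whole cohort. Narrow the section 10.2 sentence so that item 4 is not a treatment comparison.
- Make sure the CRF records the date and clock time of randomisation. The protocol says that presentation-to-first-dose timing is collected but does not say that randomisation time is. Because the drug is dispensed immediately after randomisation, first-dose time is a close proxy if randomisation time is missing, except for any woman randomised but never dosed.

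The cost is a change of wording and, if it is not already there, one CRF field. Sample size, visits and procedures are unaffected.
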